14.7 Secondary and Exploratory analyses

In a secondary analysis, a similar mixed model as described above will be fit that includes the subset of participants who are receiving treatment (dupilumab or placebo) for both nostrils. This model will incorporate nesting factors to identify repeated measures by subject and by nostril.

In an exploratory analysis, we will also compare the proportion of participants whose modified Lund- Kennedy score improved by greater than or equal to 2 units. For participants who undergo sinus surgery for AFRS prior to Week 52, non-responder imputation will be used. We will utilize a Chi-square or Fisher's exact test to examine if this proportion is significantly different by treatment group (dupilumab or placebo) at 52 weeks.

For the continuous secondary outcomes (e.g. SNOT-22 score, NPS, FEV1), a mixed effects longitudinal model will be fit that includes group (dupilumab, placebo), time (randomization through post-treatment period), and their interaction term in a similar fashioned as described for the primary outcome modified Lund-Kennedy score. For the secondary outcomes that compare the number of participants requiring rescue treatment and the number of adverse events (safety) over 52 weeks, similar mixed effects models will be fit but with consideration of a Poisson distribution (as opposed to normal distribution). The mixed effects models for both primary and secondary outcomes will permit the inclusion of any significant potential confounders.

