4.1 Overall Design

This is a multi-center, randomized, double-blinded, placebo-controlled, parallel group study to evaluate the efficacy of dupilumab 300mg administered subcutaneously (SC) every 2 weeks versus placebo in participants with AFRS following planned sinus surgery.

132 participants will be randomized to receive dupilumab 300mg SC or matching placebo while on a background of intranasal corticosteroid sprays twice daily. Patients will be stratified by study site and by baseline comorbid asthma status (yes vs no). ~25% of the randomized participants will have comorbid asthma.

Eligible participants will enter a screening/run-in period on twice daily nasal saline irrigations followed by INCS spray for 2-6 weeks prior to planned sinus surgery. Participants may be consented and enrolled at any time during this 2-6 week run-in period, provided the failure of appropriate medical therapy has been documented as outlined in the inclusion criteria. Eligible participants already on study background therapy for at least two weeks may be consented and enrolled during the pre-surgery period.

Both saline irrigations/INCS and sinus surgery will be completed per standard of care (SoC) and not according to the study protocol. Patients who continue to meet eligibility criteria following surgery will be randomized 1:1 before Visit 3 (Day 0) when they receive placebo or dupilumab 300mg SC every 2 weeks. Patients will receive a total of 26 doses of IMP, via either study

personnel (Visit 3-6 at W0, 12, 24 and 36) or home-administration (W2, 4, 6, 8, 10, 14, 16, 18, 20, 22, 26, 28, 30, 32, 34, 38, 40, 42, 44, 46, 48, 50) to maintain a 2-week treatment schedule. Patient compliance will be recorded via text messages the day of scheduled home administration, as well as monthly phone calls and collection of used syringes during scheduled study visits (Visit 4-7 at W12, 24, 36 and 52). An EOT visit will be conducted at Week 52 (Visit 7). Patients will then be monitored on daily saline irrigation and INCS spray for 12-weeks to evaluate potential disease recurrence after discontinuation of IMP. An EOS visit will be conducted at Week 64 (Visit 8).

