4.7 Randomization and blinding

Randomized participants will be stratified by enrollment site. Randomization will be assigned on a 1:1 basis to treatment group (dupilumab 300 mg every 2 weeks) or placebo. The study data team will prepare a randomization list based on computer-generated random numbers retrieved using a randomization procedure available in statistical packages such as SAS. Block randomization with varying block sizes will be employed to ensure that equal numbers of treatment and placebo participants occur within strata (site) and are balanced with respect to observed and unmeasured baseline factors.

This is a double-blind investigation. Patients, treating physicians and local study personnel will not be aware of cohort allocation.

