14.1 Sample Size and Power analysis

A sample size of 66 participants per group achieves 90% power to detect a mean difference of 2 points on the modified Lund-Kennedy Endoscopic score at 52 weeks with a standard deviation of 3.5 and significance level of 0.05 using a two-tailed test. The clinically meaningful mean difference of 2 points and the standard deviation are based on previous study of mLK in a heterogeneous population with nasal polyps [5].

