14.5 Statistical Approach

All data will first be assessed by the data management staff, under direction of the lead biostatistician, for missing data and out-of-range values with basic statistical procedures such as univariate statistics (means, standard deviations, ranges, frequencies, proportions, percentiles) and graphs such as histograms, box and whisker plots, scatter plots and Q-Q plots. In addition, plots may be produced of individual and average trajectories of all repeated measures over time according to assigned treatment. All questions of data quality and integrity will be investigated before any statistical modeling, as complete and accurate data are essential for unbiased estimates and confidence intervals.

Baseline and demographic characteristics will be summarized overall for all participants and when applicable, by treatment group. Univariate summary statistics will be provided for continuous variables and frequencies for categorical variables. Graphical methods mentioned above will be used to examine distributions and identify potential influential points. Data transformations for variables may be considered. The balance of baseline measures across the two treatment groups will be compared using appropriate 2-sample tests, including Wilcoxon rank-sum and t-tests, and Fisher's exact and Pearson Chi-square tests. All analyses will be

conducted using SAS version 9.1 for Windows (SAS Institute, Inc., Cary, NC). All analyses will be two-tailed with significance level of 0.05 and conducted using the intention-to-treat principle.

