14.6 Primary Analysis

To examine changes in the co-primary outcomes, the modified Lund-Kennedy score and the incidence of oral corticosteroid utilization per participant, a mixed effects longitudinal model will be fit that includes group (dupilumab, placebo) as a between participants factor and time (randomization through post-treatment period) as a categorical within participants factor plus their interaction term. Time is treated as categorical so that we can use the group-time interactions with the time main effect to estimate and test intent-to-treat (ITT) group differences at each time point, with 52 weeks as our primary ITT test. As randomization is stratified by site, site will also be included in the model. This mixed effects model allows incorporation of a random intercept term for each subject, different numbers of measurements (in case a visit is skipped), and the choice of appropriate variance-covariance structure. The mixed model will also permit identification of any significant changes in the post-treatment period from 52 to 64 weeks. This primary mixed model will incorporate all subject's randomized.

The primary objective will be assessed by testing this null hypothesis: treatment with Dupilumab post-surgery is equivalent to treatment with placebo post-surgery at 52-week end of treatment. The additional time point at 64 weeks is included in the model to ensure efficient evaluation of both co-primary outcomes at the EOT and 12 weeks after EOT. Significant changes between weeks 52 and 64 will be examined by linear contrast. We will test the following null hypotheses against two-sided alternatives:

- H₀₁: there is a lack of difference between the changes in mLK from baseline to 52 weeks and from baseline to 64 weeks for the untreated.
- H_{02} : there is a lack of difference between the changes in mLK from baseline to 52 weeks and from baseline to 64 weeks for the treated.
- H_{03} : the treatment effect dissipates between 52 and 64 weeks.

The primary estimand for the primary endpoint is the composite/treatment policy strategy. The intercurrent events will be handled as follows:

- Undergoing sinus surgery for AFRS: data after surgery will be assigned the worst possible score (composite strategy)
- Taking SCS or other rescue medications: data collected after use will be used in the analysis (treatment policy strategy)

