- Discontinuing treatment: all data collected after discontinuation will be used in the analysis (treatment policy strategy)

We will examine the treatment effect in the subgroup of patients with unilateral disease by recording patients' time until next sinus surgery. We will investigate differences in this subgroup by examining the Kaplan-Meier curves and utilizing the log rank test of the difference between treated and non-treated. If there is a difference between survival times, we will use the Cox proportional hazard model to account for other relevant covariates such as disease severity.

The Bonferroni correction will be used to account for multiple testing and ensure Type-I error rate remains nominal.

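### The exploratory Week-52 responder test in 14.7 ignores the site strata used in randomisation, and loses some power if responder rates differ between sites

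*Combined protocol and SAP*

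**What the plan says.** **Randomisation.** Section 4.1: "132 participants will be randomized to receive dupilumab 300mg SC or matching placebo". Section 4.7: "Randomization will be assigned on a 1:1 basis to treatment group". Sections 4.7 and 14.4 use permuted blocks of varying size within site. Section 4.1 names two stratification factors, site and baseline asthma. Section 8 intends 44 participants at each of three sites and allows for imbalance.

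**Mixed model.** Section 14.6: "As randomization is stratified by site, site will also be included in the model".

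**Responder test.** Section 14.7 labels it exploratory. A responder improves by at least 2 mLK units, and revision surgery before Week 52 counts as non-response. The test is chi-square or Fisher's exact, used "to examine if this proportion is significantly different by treatment group (dupilumab or placebo) at 52 weeks". No stratum or covariate is named.

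**Revision surgery.** Section 3.2 lists a comparison of survival curves as a secondary endpoint and names no test. Section 14.6 plans Kaplan-Meier curves in the unilateral-disease subgroup, "utilizing the log rank test of the difference between treated and non-treated". A Cox model follows only if the curves differ, and site is not named in it.

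No CMH test, stratified log-rank test or site-adjusted logistic model appears in the document.

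**The concern.** Blocking within site keeps the arms balanced at each site. Between-site variation in the outcome then largely drops out of the treatment comparison. An unstratified test still counts that variation as noise, so its assumed standard error is too large whenever site is prognostic. The true false-positive rate falls below the nominal 5% and power falls with it. The plan accounts for this in the mixed model but not in the responder test.

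Site differences are plausible. Surgery, irrigations and nasal steroid follow local standard of care (4.1, 4.5.2), postoperative care may be altered by the treating physician (4.5.3), and rescue is at the physician's discretion (4.1, 4.7.5). Rescue includes revision surgery, which makes a participant a non-responder. What is at stake is the efficiency of an exploratory result, not the primary conclusion.

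**Working it through.** **1. The plan's own figure.** Section 14.1: "A sample size of 66 participants per group achieves 90% power to detect a mean difference of 2 points" "with a standard deviation of 3.5 and significance level of 0.05 using a two-tailed test".

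n = 2(1.960 + 1.282)² × 3.5² / 2² = 64.4, so 65 per group by the normal approximation. The t-test gives 65.3, so 66. Power at 66 is 90.3% (t) or 90.7% (normal). The figure reproduces. It concerns the mLK mean; the plan gives no power for responders.

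**2. Why the test becomes conservative.** Inputs from the documents: 66 per arm, 3 sites, 1:1 within site (22 per arm per site), and "All analyses will be two-tailed with significance level of 0.05". Site responder rates p_s are assumed. Under the null:

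- variance assumed by chi-square: p̄(1 − p̄) × 2/66
- actual variance: mean of p_s(1 − p_s) × 2/66
- R = actual / assumed; true size ≈ 2[1 − Φ(1.96/√R)]

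| Assumed rates | mean p_s(1 − p_s) | p̄(1 − p̄) | R | 1.96/√R | True size |
|---|---|---|---|---|---|
| 40/50/60% | 0.2433 | 0.25 | 0.973 | 1.987 | 4.7% |
| 30/50/70% | 0.2233 | 0.25 | 0.893 | 2.074 | 3.8% |
| 20/50/80% | 0.1900 | 0.25 | 0.760 | 2.248 | 2.5% |
| 10/20/30% | 0.1533 | 0.16 | 0.958 | 2.002 | 4.5% |

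With equal rates R = 1 and nothing is lost.

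**3. Simulation, common odds ratio e (about 2.7), 22 per arm per site.** 8,000 to 40,000 runs per scenario; Monte Carlo standard error of a power figure at most about 0.6 point. Entries are chi-square / Fisher / CMH. A dash means Fisher was not run.

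| Control rates by site | Type I error, % | Power, % |
|---|---|---|
| 5/10/15% | 5.0 / – / 5.0 | 51 / – / 52 |
| 10/20/30% | 4.3 / – / 4.8 | 68 / – / 70 |
| 40/50/60% | 4.2 / 2.7 / 4.6 | 77 / 72 / 78 |
| 30/50/70% | 3.5 / 2.2 / 5.1 | 71 / 65 / 75 |
| 20/50/80% | 2.2 / 1.2 / 4.9 | 58 / 50 / 69 |

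A 40,000-run repeat of the 30/50/70% case gave 72% against 75%. The simulated sizes sit close to step 2.

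**4. Simulation with blocks of 4 and 6 (assumed sizes), 40% average placebo rate, odds ratio 2.8.** 20,000 null runs and 10,000 alternative runs.

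| Placebo rates by site | Type I error, % | Power, % |
|---|---|---|
| all 40% | 5.1 / 3.6 / 5.0 | 83 / 79 / 83 |
| 28/40/52% | 4.4 / 3.2 / 5.0 | 79 / 75 / 81 |
| 19/38/63% | 3.4 / 2.4 / 4.8 | 72 / 66 / 78 |
| 11/37/72% | 2.3 / 1.5 / 5.0 | 57 / 51 / 71 |

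The first row shows that CMH costs nothing against chi-square when sites are alike. It also shows that Fisher's test is conservative with no site effect at all (3.6%).

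**5. Log-rank.** Section 2 gives one revision every 42 months. If exponential, 1 − exp(−12/42) = 24.9% have an event by 12 months. Assumed: hazard ratio 0.3, the unilateral share, and the site spread. 6,000 runs each; entries are unstratified vs site-stratified power.

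| Population | No site effect | About 11-fold hazard range |
|---|---|---|
| 30% unilateral (about 9-10 events under the null) | 27 vs 26% | 23 vs 25% |
| 50% unilateral | 45 vs 44% | 38 vs 42% |
| Whole cohort | 76 vs 75% | 69 vs 73% |

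In the whole cohort with the 11-fold range, type I error is 3.0% unstratified against 5.1% stratified.

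**The case against.** The strongest reply is that an unstratified test here is valid: its type I error is not inflated, the analysis is exploratory, and the loss exists only if site is prognostic. Several features restrain site differences. One blinded central reader scores mLK, the study summary lists nasal steroid products and doses, 4.5.3 sets a common postoperative regimen, and all five diagnostic criteria must be met at randomisation. Low responder rates are also plausible. mLK scoring starts at Week 0, after surgery, and 14.10 expects placebo participants to worsen, so few may improve by 2 units. Low rates leave less room for spread, and the loss is then about 1-2 points. All of this stands, and it limits the size of the point. It gives no reason to prefer the unstratified test, because CMH loses nothing against chi-square when sites are alike.

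A reader might infer more than the documents support:

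- *That the responder test is too conservative as a fact.* No site-level rates are given, so this is conditional.
- *That 14.6 requires site in every analysis.* Its sentence concerns the mixed model only.
- *That the whole gap between Fisher and CMH comes from the missing strata.* Part of it is inherent to Fisher's test.
- *That the reported intervals are wrong.* Section 14.7 specifies no interval for the responder comparison.
- *That the log-rank test in 14.6 suffers equally.* It covers only the unilateral subgroup. Laterality is not a stratification factor, and events are few. Stratifying there changes power by about −1 to +4 points; low power comes mainly from event numbers.

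**Conclusion.** The point holds as an efficiency improvement to an exploratory analysis. The responder test leaves out a factor used in randomisation and in the mixed model. The cost in chi-square power is nil if sites are alike, about 1-2 points for modest site differences or low responder rates, and about 3-11 points for assumed spreads from 30/50/70% to 20/50/80%. The most extreme spread tried (11/37/72%) costs 14 points. These figures rest on assumed rates, a common odds ratio of about 2.7-2.8 and three equal sites. The co-primary analyses already include site and are unaffected.

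For revision surgery, the gap is that 3.2 names no test for the whole-cohort curves. Stratifying by site there costs under 1 power point when sites are alike and gains about 4 under a very wide spread. No change is required to the unilateral-subgroup log-rank test.

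**What to change.** 1. Reconcile 4.1 (site and asthma) with 4.7 and 14.4 (site only), and state the strata actually used. If asthma is included there are six strata. At the expected 25% asthma share, 132 × 0.25 = 33 participants have asthma, about 11 per site. CMH can handle strata of that size.
2. In 14.7, replace the chi-square/Fisher test with a CMH test stratified by those factors, and report the stratified risk difference with a 95% confidence interval.
3. For the whole-cohort revision-surgery curves in 3.2, name a site-stratified log-rank test.
4. Leave the unilateral-subgroup log-rank test in 14.6 unstratified.

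The cost is a few sentences and a strata option in the program, settled before unblinding. No extra data or participants are needed.

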4.7.2 Treatment compliance

The study treatment provided for this study will be used only as directed in this Protocol. The IMP will either be administered at the study site during treatment visits (V3-6) or at home during weeks (2, 4, 6, 8, 10, 14, 16, 18, 20, 26, 28, 30, 32, 34, 38, 40, 42, 44, 46, 48, 50) to maintain a 2-week treatment schedule. Reminder text messages will be sent to all participants the day of a home-administration. Home-administration will be confirmed by recording of both confirmatory phone calls and used syringe collection.

If a home-administered IMP dose is missed and can be given within 7 days from the planned dose date, the IMP should be given. The patient's original schedule should be resumed. If the missed dose is not administered within 7 days, the IMP should not be given. This dose should be designated as a missed dose. IMP will then be given at the next date on the original schedule.

If a treatment visit needs to be rescheduled, the visit must be performed, and the IMP must be administered within 7 days of the original visit window. Investigators should make every effort to assure that no treatment visits are missed during the course of the study. A subject will be discontinued from the study if they miss either two consecutive study visits or IMP doses, or a total of three IMP doses throughout the study period. Any change from the dosing schedule will be recorded.

Investigators should also assure that participants are compliant and on a stable dose of the background INCS spray throughout study period. Any changes to background INCS spray will be recorded for subsequent analysis.

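### The primary and secondary models may admit covariates because they are significant in the trial data, with no limit to pre-dose variables and no lock before unblinding

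*Combined protocol and SAP*

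**What the plan says.** Section 14.6 (Primary Analysis) states the core model: "a mixed effects longitudinal model will be fit that includes group (dupilumab, placebo) as a between participants factor and time", with the interaction. It adds one more fixed term: "As randomization is stratified by site, site will also be included in the model". Week 52 is the primary test.

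Section 14.7 is titled for secondary and exploratory analyses, but its last sentence covers the primary outcomes too: "The mixed effects models for both primary and secondary outcomes will permit the inclusion of any significant potential confounders". The documents do not say what must be significant (association with outcome, or imbalance at baseline), at what level, from which list, measured when, or decided when.

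Four other statements bear on this:

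- Section 14.6, on intercurrent events: "Taking SCS or other rescue medications: data collected after use will be used in the analysis (treatment policy strategy").
- Section 4.7.2, on a variable that can change after randomisation: "Any changes to background INCS spray will be recorded for subsequent analysis". Its role in the analysis is not given.
- Section 14.5: "The balance of baseline measures across the two treatment groups will be compared using appropriate 2-sample tests". No link to covariate choice is stated.
- Section 4.1: "Patients will be stratified by study site and by baseline comorbid asthma status (yes vs no"). Sections 4.7, 14.4 and 14.6 name site only.

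**The concern.** In a randomised trial a baseline covariate earns its place because it predicts the outcome and was named in advance. A significance test in the trial data is not a good reason to include it. As worded, the rule leaves the model behind the week-52 test open in two ways.

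- **Timing of measurement.** Variables recorded after the first dose are not excluded. Rescue and oral steroid use are recorded throughout. Section 14.10 expects more rescue use on placebo, so the plan itself treats it as a consequence of treatment. Oral steroid use is also the other co-primary outcome. Conditioning on it would remove part of a real effect on mLK, or produce an apparent one where none exists.
- **Timing of choice.** Nothing requires the covariates to be fixed before unblinding, so the final model could be settled with the treatment result in view.

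**Working it through.** **Plan's own figure.** Section 14.1 gives 66 per arm, a difference of 2, SD 3.5, 90% power and "significance level of 0.05 using a two-tailed test".

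- n per arm = 2 × (1.96 + 1.2816)² × 3.5² / 2² = 64.4, so 65.
- At 66 per arm, SE = 3.5 × √(2/66) = 0.609 and 2/0.609 = 3.28. Power = Φ(3.28 − 1.96) = 0.907, or 0.903 with the noncentral t.

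The stated figure is reproduced. All results below use two-sided 0.05 without the Bonferroni correction.

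**Post-dose covariate: mechanism.** In least squares at week 52:

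adjusted effect = unadjusted effect − s × (mean courses on drug − mean courses on placebo),

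where s is the within-arm slope of mLK on steroid courses. The Background gives about three courses a year. If the drug halves them, the difference in means is 1.5 − 3 = −1.5. The documents give no value for s, nor for how strongly severity drives both variables, so these are assumptions shown as a range.

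**Steroid-course count** (simulated, 66 per arm, SD 3.5, Poisson courses sharing a severity term with mLK). With courses halved:

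| Severity share of mLK variance | True −2.0 becomes | Power | Null rejection |
|---|---|---|---|
| 50% (log-rate SD 0.5) | about −0.9 | 32% | 44% |
| 25% | −1.24 to −1.38 | 50–54% | 16–23% |
| 10% | −1.50 to −1.61 | 65–69% | 9–12% |

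The first row agrees with the identity: s = 1.1/1.5 = 0.73 points per course gives −2.0 + 1.5 × 0.73 = −0.9. With no mLK effect it gives a false +1.1. If courses fall by only 25%, the difference in means is −0.75, and the same slope gives −2.0 + 0.75 × 0.73 = −1.45. In the simulations with that smaller reduction, power stays at 74% or above and null rejection at 17% or below.

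Over the whole grid (10–50% of variance, courses cut by 25–50%) the estimate runs from −0.91 to −1.87, power from 32% to 88%, and null rejection from 5% to 44%.

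**Yes/no rescue variable** (4,000 trials per setting; probit shift −0.5 to −1.0; severity correlation with mLK 0.5 to 0.7). A true −2.0 becomes −1.72 to −1.26. Power is 82% to 57% and null rejection 7% to 24%. The variable is itself significant in 88% to 99.9% of trials, so a significance rule would usually admit it.

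**Dependence on the contrast.** These figures are for the raw week-52 difference. Section 3.1 defines the endpoint as change from baseline. In a balanced longitudinal model with baseline as a response, a per-subject course count entered as a main effect shifts every visit equally and cancels from the change. The change contrast stayed at −2.00 with and without it, while the raw week-52 difference moved from −2.07 to −0.97.

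**Baseline covariates only, no treatment effect** (66 per arm; Monte Carlo error about 0.4 points).

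- Kept by significance against outcome: 5.2% error with 4 candidates explaining 20% of variance, and 6.3% with 6 candidates explaining 30%.
- Set with the smallest treatment p-value among all 2⁴ = 16 or 2⁶ = 64 subsets: 10.8% and 16.6%.
- Ten candidates, three prognostic: 4–5% for each fixed rule, 9.8% for the best of the models allowed.

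**The case against.** The strongest reply is that the plan never says it will adjust for steroid or rescue use. A variable affected by treatment is a mediator, and the word used is confounder, which strictly means something that precedes treatment. Section 14.6 handles rescue by treatment policy, and oral steroid use is a co-primary outcome. Both argue against such an adjustment. The verb can also be read as describing what a mixed model is able to do. This stands as evidence of likely intent. It does not close the rule, because no section limits covariates to pre-dose values or fixes them before unblinding.

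A reader might also infer a chain in which the baseline tests of Section 14.5 select the covariates and the spray changes of Section 4.7.2 are kept to be adjusted for. The documents do not say so. The first is a balance check with no stated consequence, and the second gives no analysis role.

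A reader might take −0.9 with 32% power, or 44% false rejection, as the expected damage. Those figures come from the most damaging corner of an assumed grid and from the raw week-52 difference. Nor does the plan authorise picking the model with the best treatment result. It only fails to rule that out.

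**Conclusion.** The concern holds as a gap in prespecification. Covariates of the primary model may be chosen by significance in the trial data, with no pre-dose limit and no lock. It does not show that the plan intends a biased adjustment.

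The size depends on what is admitted. A post-dose steroid or rescue variable could cost anything from little to more than half of the week-52 difference, and would contradict the stated estimand. That range rests on assumed severity links and on the raw week-52 contrast; a change-from-baseline contrast with a subject-level main effect would be largely spared. Significance selection among baseline variables alone does little harm. The larger inflation needs the choice to be made after seeing treatment results.

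The change is worth making because it removes all these routes at almost no cost.

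**What to change.** Delete the last sentence of Section 14.7 and state in Section 14.6, for the primary and secondary models:

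- Covariates are measured before the first IMP dose and fixed before unblinding.
- They are the randomisation factors (site, and baseline asthma once Section 4.1 is reconciled with Sections 4.7, 14.4 and 14.6) plus one baseline severity measure already collected.
- That measure is the baseline value of the outcome or, as an option, the preoperative Lund-Mackay score.
- Covariates are entered so that they act on the week-52 contrast, for example with a covariate-by-time term. A main effect alone would cancel from a change contrast.
- No variable measured after the first dose is a covariate. Any other adjusted model is a sensitivity analysis.

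Keep the baseline table descriptive and do not use its tests to choose covariates.

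The Lund-Mackay score is needed for entry, but the CT may be up to 6 months old and its correlation with week-52 mLK is unknown. If that correlation were 0.3 or 0.5, the residual SD would be 3.5 × √(1 − 0.3²) = 3.34 or 3.5 × √(1 − 0.5²) = 3.03, and power would rise from 90.3% to 92.7% or 96.4%.

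The cost is SAP wording and the loss of freedom to add covariates later.
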